### STUDY METHODS

#### 3.1 Standard of Care Treatments

Subjects enrolled may be receiving a range of medical therapies as recommended by evidence-based guidelines. The investigator or qualified designee is responsible for verifying compliance in source documentation and ensuring that any other treatments delivered are according to the local standard of care. Standard of care treatments/parameters in the context of this study include:

- 1. Aspirin: 325 mg loading dose followed by 81 mg qd.
- 2. Ticagrelor: 180 mg loading dose administered in the catheterization laboratory before the start of the PCI followed by 90 mg bid.
- 3. Cangrelor: administered in the catheterization laboratory immediately prior to PCI- before guidewire is placed in the vessel (30 ug/kg bolus followed by 4ug/kg/min infusion for 2

hours)

- 4. Tirofiban: administered in the catheterization laboratory immediately prior to PCI- before guidewire is placed in the vessel
  - (25 ug/kg bolus followed by 0.15 ug/kg/min (CrCl>60ml/min) or 0.075 ug/ml/min (CrCl<60 ml/min infusion for 2 hours).
- 5. Unfractionated heparin (UFH) in tirofiban arm: as needed (e.g., 2,000 to 5,000 U) to achieve an ACT of 200 to 250 s.
- 6. Unfractionated heparin in the cangrelor arm: as needed to achieve an ACT of 250 to 300 s for HemoTec, 300 to 350 s for Hemochron

Subjects who were prescribed medications by his/her main provider that are prohibited during the study (see section 3.2) will be excluded or exited from the study.

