## 2.4. Number of Subjects and Randomization procedure

Sixty patients with NSTEMI undergoing PCI will be randomized to receive 1:1 tirofiban or cangrelor. Allocation of study treatment will be performed via a web-based interactive randomization system, based on a computer-generated random sequence with a random block size.

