# **5.1 Timing of Assessments**

## 5.1.1 Baseline/Pre-study drug infusion

Subjects will be pre-screened to ensure that the subject is eligible for the study. During the baseline visit, the following will be completed and documented in the Case Report Forms (CRF):

- Obtain written informed consent
- Complete inclusion/exclusion criteria
- Obtain demographic information (i.e. date of birth, gender, and race)
- Record medical history (including medical, surgical, and smoking history)
- Record concomitant medications
- Obtain height and weight
- Obtain and record pre-intervention vital signs
- Obtain urine specimen for pregnancy test, if applicable
- Obtain blood specimen for platelet activation, aggregation, and biomarkers, clot strength and clot characteristics prior to study drug infusion (baseline)

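### Section 3.1 gives the two tirofiban infusion rates in incompatible units, so the rate for creatinine clearance below 60 ml/min cannot be converted to a delivered dose as written

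*Combined protocol and SAP*

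**What the plan says.** Section 3.1 lists the treatments given in the study. Item 4 covers tirofiban. It opens with a weight-based bolus of 25 ug/kg and then sets the infusion, with an alternative rate for lower creatinine clearance, as "0.15 ug/kg/min (CrCl>60ml/min) or 0.075 ug/ml/min (CrCl<60 ml/min infusion for 2 hours". Item 3 gives the comparator, cangrelor, as "30 ug/kg bolus followed by 4ug/kg/min infusion for 2" hours.

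Other parts of the protocol bear on how this line is read:

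- Section 2.4 makes tirofiban one of two randomised arms: "Sixty patients with NSTEMI undergoing PCI will be randomized to receive 1:1 tirofiban or cangrelor".
- The exclusion criteria in section 2.8 contain no renal criterion.
- Section 3.4.1 places the primary endpoint, aggregation with 20 uM TRAP, at 30 minutes after the infusion starts, which is inside the 2-hour infusion.
- Section 5.1.1 includes "Obtain height and weight" among the baseline procedures, so a per-kg rate can be applied.

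In the text reviewed, no other section restates the tirofiban rate or gives a solution concentration or infusion volume. The synopsis contains a figure that was not available in that text. If it shows a rate, that rate also needs to agree with item 4.

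**The concern.** A rate in ug/kg/min becomes a delivered amount once the patient is weighed. A rate in ug/ml/min does not: it needs a volume, and body weight plays no part in it. One line therefore gives two alternatives that cannot be put on a common scale, and one of them cannot be carried out as printed.

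What is at stake is the clarity of an intravenous antiplatelet regimen in patients with reduced creatinine clearance. Section 1 describes NSTEMI patients as typically older, with more comorbidity and a high bleeding risk, so the lower band is unlikely to be empty. There is also a point of conduct. Section 7.3 provides for audits of protocol adherence and of units of measure, and section 10.2 restricts deviations. Neither can be applied to a rate whose unit cannot be interpreted.

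**Working it through.** The protocol derives no figure here, so there is none to reproduce. The check is one of dimensions.

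**Inputs, all from section 3.1, items 3 and 4**

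| Quantity | As printed | Basis |
|---|---|---|
| Tirofiban bolus | 25 ug/kg | per kg |
| Tirofiban infusion, CrCl above 60 | 0.15 ug/kg/min | per kg |
| Tirofiban infusion, CrCl below 60 | 0.075 ug/ml/min | per ml |
| Cangrelor bolus | 30 ug/kg | per kg |
| Cangrelor infusion | 4 ug/kg/min | per kg |
| Duration of infusion | 2 hours = 120 min | |

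Four of the five dose figures are per kg, and one is not.

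**Upper band.** Infused amount = rate x weight x time = 0.15 x W x 120 = 18 x W ug. The protocol gives no weights, so W is assumed:

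- 60 kg: 18 x 60 = 1,080 ug
- 80 kg: 18 x 80 = 1,440 ug
- 100 kg: 18 x 100 = 1,800 ug

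This rate can be computed for any patient.

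**Lower band.** Rate x time = 0.075 ug/ml/min x 120 min = 9 ug/ml. That is a concentration, not an amount. Turning it into micrograms needs a volume in ml, which the protocol does not supply.

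**Comparing the two rates.** 0.15 ug/kg/min divided by 0.075 ug/ml/min = 2 ml/kg. The quotient carries units, so the text as printed does not define how one rate relates to the other.

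**How much of the dose is affected at the primary time point.** The bolus has no CrCl condition and is the same in both bands. In the upper band, the infusion has delivered 0.15 x 30 = 4.5 ug/kg by 30 minutes. The cumulative dose is 25 + 4.5 = 29.5 ug/kg, and the infusion makes up 4.5 / 29.5 = about 15% of it. The corresponding share in the lower band cannot be computed, because it depends on the rate in question. The unambiguous bolus is nevertheless given there in full.

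**Boundary.** The bands are CrCl strictly above 60 and strictly below 60. At CrCl = 60 neither condition is true, so no rate is assigned. This is independent of the unit problem. The lower rate could not be computed even if the bands met, and the gap would remain even if the units agreed.

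**The case against.** The strongest reply is that this is an evident typing slip. Every other bolus and infusion rate in items 3 and 4 is per kg, weight is collected at baseline, and ml/min stands next to the figure as the unit of creatinine clearance. A clinician would probably query a rate per ml of an unnamed volume rather than infuse it. That stands, and it lowers the chance of an unnoticed dosing error. It does not make the line correct: the reader must still infer the unit of an intravenous infusion.

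A second reply is that dosing may come from elsewhere. Section 3.1 is headed as standard-of-care treatment, and section 11 says that no investigational product is involved and leaves treatment to the main provider. This stands in part. A reader might infer that infusions are prepared from this line and that patients would be misdosed, but the protocol does not describe infusion preparation or name the source of the orders, so that inference is not supported. The defect remains because section 2.4 randomises patients to tirofiban and section 3.1 names no other dosing source.

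A third reply concerns the boundary. The protocol uses inequality signs loosely elsewhere: section 2.5.1.2 says over 18 years where section 2.7 says 18 or older, and the BARC 3a and 3b definitions in section 3.4.5 both include a hemoglobin drop of exactly 5 g/dL. A sign could also have been lost in the PDF text, although such signs survive in the BARC section. The gap concerns a single value and is rightly treated as a minor clarification. A lost sign would not explain a per-ml unit.

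**Conclusion.** Wrong as written: an internal inconsistency in an operative dosing line. The infusion rate for CrCl below 60 ml/min is in a unit that cannot be converted to a delivered dose from anything in the protocol, and it conflicts with the per-kg units around it.

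The scope is limited to the infusion component in tirofiban patients in the lower band. Planned enrolment in that arm is 30. How many of them fall below 60 ml/min is unknown, because no CrCl distribution is given. The unassigned value of exactly 60 ml/min is a separate and smaller defect, and it has no bearing on whether the rate can be calculated.

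A reader might infer that exposure in the tirofiban arm is undefined and that the primary comparison is therefore compromised. The protocol does not support that. The bolus is clear for every patient, the upper-band rate is clear, and in that band the infusion is only about 15% of the cumulative dose at 30 minutes. Nothing in the protocol allows an effect on TRAP-induced aggregation to be estimated, and no actual dosing error is shown.

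The conclusion rests on section 3.1 being the only statement of the tirofiban regimen. The body weights of 60 to 100 kg are illustrative assumptions, and the conclusion does not depend on them.

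**What to change.** The sponsor should reconcile the units of the two infusion rates in section 3.1, item 4 against the dosing source on which it relies, and state both so that each can be converted to a delivered dose. As a minor clarification in the same edit, the CrCl bands should be reworded so that every value falls in exactly one of them. This review does not say which rate or boundary is right. That is for the sponsor and the investigator to settle.

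The cost is a correction to one line of the protocol. The sample size, endpoints, assessment schedule and analysis are unchanged.

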## 3.2 Medications/Therapies Prohibited During the Study

The medications/therapies prohibited during the study are warfarin, anticoagulant other than UFH, oral direct anticoagulants, P2Y12 receptor blockers other than ticagrelor or cangrelor, glycoprotein IIb/IIIa inhibitors other than tirofiban. Potential and enrolled subjects on or started on prohibited medications will be excluded or exited from the study.

# 3.3 Laboratory Measurements

Phlebotomy sites will be carefully chosen to minimize risk and platelet activation. After discarding the first 2-3 mL of free flowing blood, the blood collection tubes will be filled to capacity and gently inverted 3 to 5 times to ensure complete mixing of the anticoagulant. Tubes containing 3.2% trisodium citrate and hirudin will be used for flow cytometry, light transmittance aggregometry, thrombelastography, and shear-induced platelet aggregation.

# • Platelet Aggregation

Platelet aggregation will be assessed in platelet-rich plasma using a Chronolog Lumi-Aggregometer (model 490-4D) with the AggroLink software package after stimulation with 5 and 20uM ADP, 4ug/ml collagen and 15 and 20uM TRAP).

### • Platelet Activation

Expressions of p-selectin, and annexin binding will be assessed by flow cytometry using respective antibodies at baseline, and 1 hour and 12-24 hour after the end of the infusion.

### • Platelet-Fibrin Clot Characteristics

Plate-fibrin clot characteristics will be assessed by the TEG6s instrument. TEG6S is a microfluidic fully automated cartridge-based device that provides quantitative and qualitative measurements of the physical properties of a clot. We will assess thrombin- and ADP-induced platelet-fibrin-clot strength, time to initial thrombin generation, and functional fibrinogen

## • Shear-Induced Platelet Aggregation:

Shear-induced platelet aggregation by novel T-TAS® plus system.

#### • Thrombin Generation Kinetics:

Time to peak thrombin generation, peak thrombin generation, and total thrombin

generation kinetics will be assessed by Calibrated Automated Thrombogram (CAT). These parameters will be assessed at baseline and 10 minutes post-start of the infusion.

# • High Sensitivity Troponin and CK-MB:

High sensitivity troponin and CK-MB will be assessed at baseline, and 2 hour, 4-6 hour and 12-24 hour after the end of the infusion.

# 3.4 Primary and Secondary endpoints

# 3.4.1 **Primary Endpoint**

Relative difference in 20 uM TRAP-induced platelet aggregation between cangrelor and tirofiban therapy at 30 minutes post-start of the infusion.

# 3.4.2 **Secondary Endpoints**

- Relative differences in 15 and 20  $\mu$ M TRAP- induced platelet aggregation by light transmittance aggregometry between cangrelor and tirofiban therapy at all post-infusion time points except stated above.
- Relative differences in ADP and collagen-induced platelet aggregation by light transmittance aggregometry between cangrelor and tirofiban therapy at all post-infusion time points.
- Relative differences in P-selectin, and annexin binding between cangrelor and tirofiban therapy at 1 h and 12-24h after the end of the infusion.
- Relative differences in thrombin- and ADP-induced platelet-fibrin-clot strength, time to initial thrombin generation, and functional fibrinogen between cangrelor and tirofiban therapy at all post-infusion time points.
- Relative differences in shear-induced platelet aggregation between cangrelor and tirofiban therapy at all post-infusion time points.
- Relative differences in time to peak thrombin generation, peak thrombin generation and total thrombin generation between cangrelor and tirofiban therapy at 10 minutes post-infusion time point.
- Relative differences in peak high sensitivity troponin and CK-MB between cangrelor and tirofiban therapy will be assessed at 2 hour, 4-6 hour and 12-24 hour post-infusion time points.

# 3.4.3 Clinical Endpoints

Patients will be followed for clinical outcomes. All AEs and SAEs will be collected from randomization through 48 hours (+24 hours) after randomization. If there is a delay between time of randomization and start of study drug, AEs will be collected from time of randomization through 48 hours (+24) after study drug initiation. If a subject is discharged from the hospital prior to the 48 hour (+24 hour) assessment time-frame, subjects will receive a telephone call to review AEs and SAEs.

### 3.4.4. Adverse Events

Patients will be carefully monitored for AEs by the investigator during the designated study period. AEs and the treatment provided during the study should be recorded in the patient's treatment record and eCRF. Those events that are serious in nature will be reported to Medicure in an expedited manner. Patients experiencing AEs will be followed clinically until their health has returned to baseline status or until all parameters have returned to

normal or have otherwise been explained. The investigator will provide or arrange appropriate supportive care for the patient if necessary.

### **Adverse Event**

An AE is defined as any untoward medical occurrence in a patient administered a medicinal product and which does not necessarily have to have a causal relationship with this treatment. An AE can therefore be any unfavorable and unintended sign (including an abnormal laboratory finding), symptom or disease temporally associated with the use of amedicinal product, whether or not considered related to the medicinal product.

#### **Serious Adverse Event**

A serious adverse event (SAE) is any untoward medical occurrence that: Results in death,

Is life-threatening, i.e., the subject was, in the opinion of the investigator, at immediate risk of death from the event as it occurred.

Results in persistent or significant disability/incapacity,

Requires in-patient hospitalization or prolongs hospitalization,

Is a congenital anomaly/birth defect, or

Is another medically significant event that, based upon appropriate medical judgment, may jeopardize the subject and may require medical or surgical intervention to prevent one of the outcomes listed above

Severity is an estimate or measure of the intensity of an AE, while the criteria for serious AEs are indications of adverse patient outcomes for regulatory reporting purposes. A severe AE need not necessarily be considered serious and a serious AE need not be considered severe. For example, nausea that persists for several hours may be considered severe nausea, but not an SAE. On the other hand, an MI that may be considered minor could also be an SAE if it prolonged hospitalization.

# 3.4.5. Bleeding

Bleeding will be assessed by the BARC scale. Bleeding will be assessed from the time of randomization through 48 hours after study drug initiation.

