#### 2 STUDY DESIGN AND SUBJECT SELECTION

#### 2.1 Study Type

This is a single center open label, randomized, observational study.

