### **BARC** criteria:

- Type 0: no evidence of bleeding.
- Type 1: bleeding that is not actionable and does not cause the patient to seek unscheduled performance of studies, hospitalization, or treatment by a healthcare professional. Examples include, but are not limited to, bruising, hematoma, nosebleeds, or hemorrhoidal bleeding for which the patient does not seek medical attention. Type 1 bleeding may include episodes that lead to discontinuation of medications by the patient because of bleeding without visiting a healthcare provider.
- Type 2: any clinically overt sign of hemorrhage (eg., more bleeding than would be expected for a clinical circumstance, including bleeding found by imaging alone) that is actionable but does not meet criteria for type 3, type 4 (CABG-related), or type 5 (fatal bleeding) BARC bleeding. The bleeding must require diagnostic studies, hospitalization, or treatment by a healthcare professional. In particular, the bleeding must meet at least

one of the following criteria: First, it requires intervention, defined as a healthcare professional—guided medical treatment or percutaneous intervention to stop or treat bleeding, including temporarily or permanently discontinuing a medication or study drug. Examples include, but are not limited to, coiling, compression, use of reversal agents (eg, vitamin K, protamine), local injections to reduce oozing, or a temporary/permanent cessation of antiplatelet, antithrombin, or fibrinolytic therapy. Second, the bleeding leads to hospitalization or an increased level of care, defined as leading to or prolonging hospitalization or transfer to a hospital unit capable of providing a higher level of care. Or third, the bleeding prompts evaluation, defined as leading to an unscheduled visit to a healthcare professional resulting in diagnostic testing (laboratory or imaging). Examples include, but are not limited to, hematocrit testing, hemoccult testing, endoscopy, colonoscopy, computed tomography scanning, or urinalysis. A visit or phone call to a healthcare professional during which neither testing nor treatment is undertaken does not constitute type 2 bleeding.

- Type 3: clinical, laboratory, and/or imaging evidence of bleeding with specific healthcare provider responses, as listed below:
- Bleeding Academic Research Consortium type 3a bleeding Any transfusion with overt bleeding

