Overt bleeding plus hemoglobin drop  $\geq 3$  to  $\leq 5$  g/dL (provided hemoglobin drop is related to bleeding). Hemoglobin drop should be corrected for intracurrent transfusion in which 1 U packed red blood cells or 1 U whole blood would be expected to increase hemoglobin by 1 g/dL.

Bleeding Academic Research Consortium type 3b bleeding
 Overt bleeding plus hemoglobin drop ≥5 g/dL (provided hemoglobin drop is related to
 bleed). Hemoglobin drop should be corrected for intracurrent transfusion in which 1 U
 packed red blood cells or 1 U whole blood would be expected to increase hemoglobin by
 1 g/dL.

Cardiac tamponade

Bleeding requiring surgical intervention for control (excluding dental/nasal/skin/hemorrhoid)

Bleeding requiring intravenous vasoactive drugs

Bleeding Academic Research Consortium type 3c bleeding
 Intracranial hemorrhage (does not include microbleeds or hemorrhagic transformation; does include intraspinal); subcategories confirmed by autopsy, imaging, or lumbar puncture.

Intraocular bleed compromising vision

 Type 4: Coronary Artery Bypass Graft—related bleeding Perioperative intracranial bleeding within 48 hours Reoperation after closure of sternotomy for the purpose of controlling bleeding

\_\_\_\_\_

Transfusion of ≥5 U whole blood or packed red blood cells within a 48-hour period (only allogenic transfusions are considered transfusions for CABG-related bleeds) Chest tube output  $\geq 2$  L within a 24-hour period

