## 5.1.2 Post-start of study drug infusion

Subjects are expected to be seen as an inpatient during the study. Time-points for this period include 10 minutes and 30 minutes post-start of the infusion and 30 minutes, 1 hour, 2 hour, 4-6 hour, and 12-24 hour post-end of study drug infusion (a 10% window at each time point is acceptable). During these time points, blood specimens for platelet activation, aggregation, clot characteristics, and biomarkers, will be obtained. If applicable, urine

specimen for pregnancy test will be obtained at 12-24 hours post-end of drug infusion. Continued eligibility, changes in concomitant medications, and subject status will be collected.

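### BARC types 3a and 3b have routes that need a hemoglobin drop, but no hemoglobin is scheduled in this open-label trial, so detection by those routes may differ by arm

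*Combined protocol and SAP*

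**What the plan says.** Section 3.4.5 adopts BARC ("Bleeding will be assessed by the BARC scale") and sets the window: "Bleeding will be assessed from the time of randomization through 48 hours after study drug initiation". The criteria that follow include, for type 3a, overt bleeding with a transfusion-corrected hemoglobin drop of at least 3 and at most 5 g/dL. For type 3b they include "Overt bleeding plus hemoglobin drop ≥5 g/dL", corrected in the same way.

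The baseline list in 5.1.1 asks for blood for platelet, biomarker and clot assays. After the start of infusion, 5.1.2 says that "blood specimens for platelet activation, aggregation, clot characteristics, and biomarkers, will be obtained". Neither list, nor the Laboratory Assays list in the synopsis, nor the methods in 3.3, names hemoglobin, hematocrit or a blood count. Hematocrit appears in two other places: exclusion 12, which concerns anemia already known, and the type 2 text, as an example of testing that a bleed may prompt ("Examples include, but are not limited to, hematocrit testing, hemoccult testing, endoscopy").

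On blinding, section 2.1 reads: "This is a single center open label, randomized, observational study". No blinded grading of bleeding is described.

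**The concern.** A drop is a difference between two measurements. If the protocol schedules neither, the hemoglobin routes to 3a and 3b operate only in patients whose treating team obtained a value both before and after the bleed. That team knows the treatment. If it checks more readily in one arm, that arm can show more hemoglobin-defined type 3 bleeding at the same true blood loss.

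At stake is whether BARC grades can be compared between two intravenous antiplatelet regimens. Section 7.2 also has safety data reviewed after every 10 subjects, to decide whether the study continues, is modified or closes enrollment. It does not name BARC grades, but bleeding would ordinarily be part of such data.

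A separate, smaller point is that the printed 3a and 3b ranges share an end point, so one value has two grades.

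**Working it through.** The documents give no bleeding rate, testing rate or power for bleeding, so there is no stated figure to reproduce. The check sets the passages side by side, with simple arithmetic for scale.

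**1. Which routes need a hemoglobin value (BARC criteria under 3.4.5).**
- Need one: type 3a by a drop of 3 to 5 g/dL; type 3b by a drop of 5 g/dL or more.
- Do not need one: type 3a by transfusion with overt bleeding; type 3b by tamponade, surgical control or intravenous vasoactive drugs; types 3c, 4 and 5.

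**2. Whether the plan supplies the value.**
- Synopsis assay list and section 3.3: aggregometry, flow cytometry, TEG6s, T-TAS, thrombin generation, troponin and CK-MB. No hemoglobin.
- 5.1.1 and 5.1.2: blood for the same classes of assay, plus a urine pregnancy test where applicable. No hemoglobin.
- Exclusion 12: known anemia only, so it does not oblige anyone to measure a baseline value.
- 3.4.3: patients discharged early are followed for adverse events by telephone, which yields no hemoglobin.

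The plan therefore guarantees neither the before value nor the after value.

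**3. How much of the bleeding window the existing draws could cover.** Both infusions last 2 hours (3.1), and the last draw is 12-24 h after the end of infusion.
- Time from drug start to last draw: 2 + 12 = 14 h to 2 + 24 = 26 h.
- Remainder of the 48 h window: 48 − 26 = 22 h to 48 − 14 = 34 h.

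A value on the last draw gives both arms the same minimum detection but does not span the window.

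**4. Scale.** With 30 per arm, one patient moves an arm's rate by 1/30 = 3.3 percentage points.

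The following is an assumption, not an estimate. Let p be the true rate, equal in both arms, of overt bleeding with a qualifying drop and no other route to type 3. Let t1 and t2 be the proportions of those cases with both values available.

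Recorded rate = p × t; spurious gap = p × (t1 − t2).

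| p | t1 vs t2 | Recorded | Gap (points) | Patients of 30 |
|---|---|---|---|---|
| 5% | 90% vs 50% | 4.5% vs 2.5% | 2 | 0.6 |
| 10% | 90% vs 50% | 9% vs 5% | 4 | 1.2 |
| 20% | 90% vs 50% | 18% vs 10% | 8 | 2.4 |
| 5% | 80% vs 60% | 4% vs 3% | 1 | 0.3 |
| 10% | 80% vs 60% | 8% vs 6% | 2 | 0.6 |
| 20% | 80% vs 60% | 16% vs 12% | 4 | 1.2 |

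If t1 = t2, as with a common schedule, the gap is 0.

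**5. Overlap of 3a and 3b.** With d the corrected drop, 3a requires 3 ≤ d ≤ 5 and 3b requires d ≥ 5. Both hold only at d = 5; on a 0.1 g/dL grid that is the single value 5.0. Making either bound strict removes the overlap.

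**The case against.** The strongest reply is that these are inpatients having PCI for NSTEMI, so routine care may well supply hemoglobin values, and section 7.3 has medical records and laboratory results audited with the case report forms. Detection then need not rest wholly on a team that knows the arm. This narrows the point but does not remove it: the plan neither requires, times nor asks for the recording of such values, and a drop needs two of them.

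It is also fair to say that a serious bleed can reach type 3 without a hemoglobin value, for example by transfusion. That stands, and it limits the point to the two hemoglobin routes. For the same reason, a reader should not infer that an undetected drop must remain at type 1. Type 1 bleeding is by definition not actionable, and a bleed that is treated can reach type 2 without any test.

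A reader might further infer that ordering a hematocrit is enough to raise a bleed to type 2, so that unequal testing distorts type 2 as well. The documents do not support that as stated. The relevant route applies when "the bleeding prompts evaluation, defined as leading to an unscheduled visit to a healthcare professional resulting in diagnostic testing (laboratory or imaging"), and the text does not say that a blood count ordered for someone already in a hospital bed is such a visit. The companion rule, that a visit or call "during which neither testing nor treatment is undertaken does not constitute type 2 bleeding", does not settle it. A scheduled hemoglobin would not equalize clinician-ordered testing in any case.

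Finally, the overlap at 5 g/dL is small. Both grades are type 3, only one exact value is affected, and the sign for 3a should be checked against the source PDF, since the text was machine-read.

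**Conclusion.** The point holds for the hemoglobin routes of types 3a and 3b. As written, the plan leaves them dependent on whichever hemoglobin values routine care produces, in a trial where the treating team knows the arm. Detection may therefore differ between arms.

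The size of any bias cannot be computed. The gaps of 1 to 8 percentage points shown above rest wholly on assumed true rates of 5% to 20% and assumed testing proportions, and they shrink if affected patients also qualify by another type 3 route. The documents show that unequal detection is possible, not that it will occur.

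The other routes listed above and the primary endpoint (20 µM TRAP aggregation at 30 minutes) are unaffected. Nor do the documents rank bleeding as the leading safety comparison: it is not among the secondary endpoints in 3.4.2, and section 4.2 gives only general tests for categorical variables.

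The shared 5 g/dL bound is a separate, minor definitional fault. It does not make grades depend on who is tested.

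**What to change.** In 5.1.1 and 5.1.2, record hemoglobin for every patient in both arms at baseline and at the 12-24 h post-end draw. Use blood already being drawn, or transcribe the routine inpatient value nearest those times. Also record the lowest available value up to 48 hours after drug start. State in 3.4.5 that this scheduled value does not by itself count as prompted evaluation for type 2.

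As a separate correction, make the 3a and 3b hemoglobin ranges mutually exclusive at 5 g/dL, after checking the printed sign against the source PDF.

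The cost is one inexpensive laboratory value on two existing draws, or transcription instead, plus a few case report form fields and a one-symbol edit. This changes data collection only. A limit remains: drops after the last draw may still be missed, because the lowest value up to 48 hours depends on what routine care measured.
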